4.8.2 Interviews

Semi-structured interviews will be conducted to explore participants' experience with cfDNA testing, perceptions of the clinical utility of cfDNA tests for HCS management and to identify factors facilitating or impeding the uptake of this test in HCS management. The interview component of this study is optional, and patients preferences will be captured on the consent form.

All participants who receive a positive cfDNA test result and who have consented to being contacted for an interview, will be invited for an interview approximately 6-12 months following a positive result disclosure. Additional participants will be invited for an interview, from the pool of participants who have agreed to participate in the interview portion of the study. Any participant may partake in up to 3 interviews over the duration of the study. A participant can decline to participate in an interview at any time during the study. Each interview will take approximately one hour to complete and will be conducted via telephone or Zoom healthcare (participant preference).

All interviews will be audiotaped using a handheld audio recorder. Audio-recorded interviews will be sent off site for transcription by Rev.com for transcription via their secure file transfer system. All data at Rev.com is encrypted at rest and in transit (<https://www.rev.com/security>). Only de-identified interview recordings will be uploaded onto Rev.com. This de-identified data will be stored on Rev.com's USA servers during the transcription process. Rev.com does not own the audio recording and transcripts or any study data. After the transcription is complete and verified, the recordings and transcripts will be removed from the Rev.com site and server. The transcribed interviews will be managed and analysed using Dedoose (<https://www.dedoose.com/>), a web-based qualitative analysis software.

All audio recordings will be destroyed after they have been transcribed and verified for accuracy by the study team. Any identifying information such as names of individuals, institutions, or geographic locations will be removed from the audio recordings by the study team prior to sending the audio recorder for transcription. Each study participant will be assigned a unique identifier and will be referred to only by this code number in the transcript. The recording devices are password protected and will kept in a locked drawer in the study offices (at Unity Health) when not in use. Recording devices are only accessible by Unity Health study staff. Immediately after an interview has been completed, all recordings will be uploaded to secure servers at Unity Health or UHN, (identified only by study ID) subsequently the interview will be erased from the recorder. The recorder is not stored in the study offices with a recording left on it. When an interview is conducted it (whether over the phone or via Zoom healthcare) is always in

the possession of the study staff member and it is only used during the interview, which takes place in a private location.

4.9 Randomization and Measures to Minimize Bias

Cancer risks are different for the 5 HCS cohorts we will enroll in this study. Participants will be randomized into the control and experimental arms based on their HCS diagnosis, to achieve roughly the same number of participants from each HCS cohort in each arm of the study. To avoid over-stratification, we will not randomize participants based on other factors (such as age, prophylactic surgery, cancer history etc.). However, these other factors also influence cancer risks, and we will collect this information, to minimize bias in our subsequent analysis.

4.10 Blinding Methods

This study is not blinded.

4.11 Endpoints

The endpoints of this study are:

1. To assess the performance of the cfDNA assay for cancer detection in patients with HCS, including assay sensitivity, specificity, PPV, and NPV. The test performance endpoint is a diagnosis of cancer and will be assessed at multiple points during the study (at a minimum yearly). Cancer diagnosis will be confirmed by imaging, pathology, or other confirmation deemed appropriate by the treating physician.
2. To assess the time to cancer diagnosis using cfDNA sequencing compared to controls.
3. To assess the detection rate of cancer with no standard-of-care screening available (e.g., pancreatic cancer, endometrial cancer) using cfDNA sequencing.
4. To assess patient reported outcomes (including anxiety, empowerment, distress, risk perception) using validated scales administered before, during, and after the study.

4.12 Study Duration and Participant Time Commitments

The expected study duration for each participant will be approximately 5 years from the date of first sample collection (Table 1). We will do our best to minimize the number of on-site visits required by participants. Participants will have the option to provide research blood samples via their local community laboratory (e.g. LifeLabs or Dynacare). Result disclosure by the study team will be done over the phone, unless the participant is on-site for a clinical appointment, in which case results may be disclosed in person. Participants will be required to come into the hospital for diagnostic investigations done in follow-up to a “positive” cfDNA assay result.

Table 1. Participant requirements.

Activity	Year 1			Year 2			Year 3			Year 4			Year 5
Blood Collection ¹	x	x	x	x	x	x	x	x	x	x	x	x	
Test Results Returned to Participants (experimental cohort)	x	x	x	x	x	x	x	x	x	x	x	x	
Follow-up Diagnostic Investigations (experimental cohort)	Diagnostic investigations will ensue following a “positive” cfDNA assay result.												
Medical History and Demographic Questionnaire ²	x												
Patient-Outcome Questionnaire	x	x	x	x	x	x	x	x	x	x	x	x	
Collection of clinical data by study team.	Clinical data will be collected by the study team for up to 7 years from the date of study enrollment.												
Interviews (optional)	Interviews will be conducted over the course of the study. They will begin at the end of year 1.												

¹Tri-annual blood collection is only a study requirement for those randomized into the experimental cohort. Those in the control cohort have the option to provide up to 3 blood samples a year, ² The medical history questionnaire will be completed at least once by all participants at the time of study enrolment. Participants may be asked to update the questionnaire over the course of the study.

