Participants will be asked to provide an additional blood sample after a “positive” cfDNA result, which will be transferred to OICR and analyzed (in the same methods as outlined earlier). The results of this additional test may not be returned to the participant, and will primarily be used by the study team to correlate with the previous result, and to rule out the possibility of a technical error/lab mix-up. Additionally, some of the blood sample will be used for clinical testing (CBC, tumor markers etc), as indicated in the cohort specific follow-up diagnostic workflows (appended).

The follow-up diagnostic investigations for a “positive” cfDNA test result, for each HCS cohort, are outlined in “Cohort Specific Diagnostic Workflows”, appended to this protocol. These workflows were developed together with clinicians who follow these patient populations. If the above diagnostic investigations do not identify a malignancy, and the participants next scheduled research blood draw result is still “positive”, a PET-CT will be performed as a final step to assess cancer status.

For participants enrolled at UHN, diagnostic investigations will be completed at UHN, whenever possible, or may be arranged at an external site if not offered at UHN. A contract will be signed with any external site used (for example, the Toronto Immune Digestive Health Institute, or In-Common Laboratories). Participants will be informed that if a diagnostic investigation needs to be completed at a non-UHN site, identifying information (including name, date of birth, OHIP number and version code) will be shared with that site.

The Study Doctor may determine that an alternative workup plan is necessary (for example, if a participant underwent relevant diagnostic investigations completed as part of their standard-of-care surveillance shortly before their blood test, a particular investigation is not available or the wait time is too long, or if the patient has any allergies which prevent a particular investigation). Any alternative workup plan will be documented by the study team. A diagnosis of cancer will be documented based on pathologic confirmation, imaging confirmation (if pathologic not possible), or by other clinical confirmation deemed appropriate by the managing clinician.

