4.8 Collection of Clinical Data

Clinical data will be collected from participants' medical record and the medical history and demographic questionnaires completed by participants following informed consent (please see "Demographics and Medical History Questionnaire"). Participants will be given the option to complete the questionnaire in person (e.g., if the consent process occurred in person), or electronically. If completed electronically, the questionnaire may be emailed to the participant, or the participant may complete the questionnaire via REDCap (a link will be emailed to them). If a patient is not able to complete the questionnaire electronically, a physical copy may be mailed to them with a return envelope. The questionnaires will record the patient's study ID only (name, DOB, MRN will not be recorded). Updates to questionnaire results may be collected by the study team over the course of the study.

If a participant receives care at more than one study site, their medical records from any of the other sites may also be looked at, regardless of which site they are enrolled at for this study. Sharing of any study records between sites for patients who have received care at multiple sites will only occur following execution of appropriate DTAs. Study team members may also request medical history information from participants directly, if not available in their medical records (e.g. by setting up a phone call). Additionally, study team members may ask a participant to complete a Release of Information (ROI) form (appended to this application), to request medical records from external hospitals/clinics.

The following clinical data will be captured over the course of this study for all participants:

- Demographic information (including date of birth, self-reported gender and sex assigned at birth, ethnicity).
- Genetic diagnosis and date.
- Past medical history, including but not limited to personal history of cancer, cancer risk factors, cancer screening history, pregnancy status, current medications, comorbidities.
- Cancer screening – results and dates of any cancer screening/diagnosis investigations done prior to, or during the study (including the diagnostic investigations done in follow-up to a positive cfDNA test result).

- For participants with a history of cancer or diagnosed with cancer during the study – pathology information, imaging and procedure results, treatment details.
- Family history of cancer.

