6.0 Study Intervention

All study participants will continue to receive standard-of-care cancer screening over the course of this study, as they have prior to study enrollment. Study participants randomized into the experimental arm will provide blood samples 3 times a year for 4 years. cfDNA sequencing will be performed on blood samples collected from participants in the experimental group. Results of the cfDNA sequencing (either “cancer signal detected” or “cancer signal not detected”) will be communicated to the participant by a designated member of the study team. We expect up to approximately 5-10% of participants per year in the experimental arm will receive a “cancer signal detected” result, which will trigger follow-up diagnostic investigations to confirm if cancer is present or not (outlined in Appendix A: “Cohort Specific Diagnostic Workflows”). The type of follow-up diagnostic investigations will be consistent with standard-of-care recommendations.

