After a potential participants is identified by a member of their circle of care (for example, the Study Doctor), study team members who are not part of a patients circle of care (Study Manager and/or Study Coordinators listed as Study Personnel in the CAPCR submission) may review a potential participant's electronic medical records at UHN to confirm study eligibility prior to study introduction by a member of their circle of care. The study team member will use the Screening Eligibility Checklist (appended to this application) to confirm eligibility. The study team member will document Yes or No for each question on the checklist. No specific health information (e.g., details of a cancer diagnosis) will be documented by the study team prior to study enrollment. If a patient is deemed ineligible, or declines enrollment, the study eligibility checklist will be destroyed, and only the patient name and month/year of birth will be retained by the study team until the end of the enrollment period. We have requested an REB waiver to allow study team members who are not part of a patients circle of care to screen the medical records as described above, to determine participant eligibility.

Participants may also be identified at the Zane Cohen Centre for Digestive Disease at Mount Sinai Hospital. A member of a potential participant's circle of care (e.g. a Genetic Counsellor) at the Zane Cohen Centre can introduce the patient to the study. If a patient is interested, their clinical team member will complete the "Study Contact Form" and email the completed form to the CHARM2 study team. The CHARM2 team member will then contact the interested participant (as outlined below). All participants recruited through Mount Sinai Hospital will be enrolled into the CHARM2 study at UHN. No study procedures (other than recruitment) will be carried out at Mount Sinai Hospital. Participant recruitment will begin at Mount Sinai Hospital only after Research Ethics Approval is received by the Mount Sinai REB.

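### No scheduled contact common to both arms asks about new cancers, while only the experimental arm has 12 result disclosures and study-initiated work-ups, so capture of cancers could differ between arms

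*Protocol*

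**What the plan says.** Section 4.8 (Collection of Clinical Data) names the sources for all participants: "Clinical data will be collected from participants' medical record and the medical history and demographic questionnaires completed by participants following informed consent". Records are followed for up to 7 years from enrolment. The same section allows the team to ask participants directly for history missing from their records, and to use a release form for outside records. Both are optional.

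The medical history form has one fixed date. Section 4.12, Table 1, footnote 2: "The medical history questionnaire will be completed at least once by all participants at the time of study enrolment". What follows has no date: "Participants may be asked to update the questionnaire over the course of the study", and in section 4.8, "Updates to questionnaire results may be collected by the study team over the course of the study".

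The experimental arm has more study contact. Section 6.0: "Study participants randomized into the experimental arm will provide blood samples 3 times a year for 4 years". Section 4.12: "Result disclosure by the study team will be done over the phone, unless the participant is on-site for a clinical appointment". After a positive result the study starts a work-up, and for UHN enrollees "diagnostic investigations will be completed at UHN, whenever possible".

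Section 4.8.1 gives both arms a patient-outcome questionnaire, after each result disclosure in the experimental arm and up to three times a year in controls. Completion is voluntary, and the measures described concern emotional outcomes. Control blood donation is optional (section 4.1). Section 4.11 promises at least yearly assessment of cancer diagnosis, but under the assay-performance endpoint. Section 4.10 states that the study is unblinded.

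Section 11.1 brings in patients from two other hospitals and enrols them at UHN. For one of them it says: "No study procedures (other than recruitment) will be carried out at Mount Sinai Hospital".

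**The concern.** A comparison of detection rates, or of time to diagnosis, is fair only if a cancer that occurs has the same chance of entering the database in either arm. The experimental arm has a dozen conversations about cancer results and a work-up pathway whose findings reach the study by design. A control treated at another hospital has no scheduled contact at which a new cancer is asked about. Whether that cancer is found depends on discretionary steps taken by staff who know the allocation.

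Here more detection counts as success for cfDNA. Under-capture in controls therefore looks like benefit. In a time-to-diagnosis analysis of all randomised participants, a missed control cancer would also be counted as cancer-free follow-up. Later analysis cannot restore diagnoses that were never collected.

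**Working it through.** **Step 1. Contact count.** Blood draws with results returned: 3 per year × 4 years = 12 in the experimental arm and 0 in controls. This agrees with Table 1.

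**Step 2. Routes by which a new cancer could become known.**

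| Route (Protocol section) | Experimental | Control | Fixed date at which new cancer is asked about? |
|---|---|---|---|
| Medical history form (4.12) | once | once | enrolment only; updates discretionary |
| Patient-outcome questionnaire (4.8.1) | after each disclosure | up to 3 a year | recurring, but voluntary and described as emotional outcomes |
| Record review, direct requests, release forms (4.8) | yes | yes | no interval or trigger per participant |
| Contact for history missing from records (11.5) | yes | yes | no interval |
| Quarterly database audit (10.0) | yes | yes | no participant contact; cannot by itself reveal an unreported diagnosis |
| Yearly assessment (4.11) | under assay performance | not stated | no method named |
| Result disclosure (4.6, 4.12) | 12 | 0 | contact exists; not said to ask |
| Study-initiated work-up (4.6, 6.0) | after a positive result, expected in up to about 5-10% a year | none | produces diagnoses directly |

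No row gives both arms a dated question about new cancer. The last two rows exist in one arm only.

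**Step 3. Size, as an illustration.** Inputs from the protocol: 500 per arm (section 4.1); a 5% rate without cfDNA, 10% as the upper scenario, a 2-point target and two-sided 0.05 (section 8.0). Assumption: the capture fractions c_E (experimental) and c_C (control), for which the documents give no figure.

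With the same true rate p in both arms, the false difference is p × (c_E − c_C).

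- Cancers per arm at p = 0.05: 0.05 × 500 = 25.
- c_E = 1, c_C = 0.90: 25 × 0.10 = 2.5 missed; controls read 22.5/500 = 4.5%; false difference 0.5 point.
- c_E = 1, c_C = 0.80: 25 × 0.20 = 5 missed; controls read 20/500 = 4.0%; false difference 1.0 point.
- Only the gap matters: c_E = 0.95 and c_C = 0.85 also give 0.05 × 0.10 = 0.5 point. Equal capture gives no false difference, and poorer capture in the experimental arm reverses the sign.

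**Step 4. Effect on the test.** Pooled two-proportion z-test with 500 per arm. Let d be the false difference, se0 the pooled standard error and se1 the unpooled one. The chance of a significant result favouring cfDNA is 1 − Φ((1.96·se0 − d)/se1). For c_C = 0.80 at 5%: d = 0.010, se0 = 0.01311, se1 = 0.01311, so (0.02570 − 0.010)/0.01311 = 1.20 and the chance is 11.6%. Total rejection in either direction, with no true effect and c_E = 1:

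| Control capture | p = 5%: difference, rejection | p = 10%: difference, rejection |
|---|---|---|
| 95% | 0.25 point, 5.4% | 0.5 point, 5.8% |
| 90% | 0.5 point, 6.6% | 1.0 point, 8.4% |
| 80% | 1.0 point, 11.9% | 2.0 points, 19.7% |
| 70% | 1.5 points, 21.7% | 3.0 points, 39.8% |

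The 2-point target is only a yardstick here. Section 8.0 claims more than 97% power for it, but the same test at 5% versus 7% with 500 per arm gives 26.5%. That is a separate problem, and this point does not depend on it.

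**The case against.** The strongest reply is that the protocol treats both arms alike where it matters. Record review, direct requests and release forms cover everyone. Section 11.5 tells all participants that they will be contacted for history missing from their records. Section 10.0 adds regular data collection and a quarterly completeness audit, and section 7.0 a monthly check on screening compliance. Disclosure calls are not said to ask about new diagnoses. Work-ups follow only positive results and may be done outside UHN. Experimental-arm cancers found by standard care reach the study by the same route as control cancers. Patients from the other hospitals are randomised to both arms, and their records may be reviewed. Timing could be left to operating procedures.

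Much of this stands, and it rules out several stronger readings that a reader might infer:

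- That the arms share no scheduled contact: they share the patient-outcome questionnaire.
- That only controls depend on record review: both arms do.
- That release forms are used only once a cancer is already suspected: section 4.8 sets no such condition.
- That control cancers would be dated late: investigation dates are collected, so learning of a cancer late does not move its diagnosis date.
- That the repeated questionnaire certainly omits cancer: the form is appended and not visible here.

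There is also a risk in the other direction. Section 5.3 allows withdrawal for non-compliance, gives experimental-arm blood draws as its example, and stops data collection afterwards. That could lose experimental cancers.

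The reply does not supply a common date or trigger for asking each participant about new cancer. Because the trial is unblinded, leaving this to discretion allows effort to differ by arm.

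**Conclusion.** The point holds as a gap in outcome ascertainment. The protocol schedules no recurring contact, common to both arms, that asks about new cancer, while one arm alone has 12 result disclosures and study-initiated work-ups. Less complete capture of control cancers diagnosed outside UHN is a plausible risk; the documents do not show that it will happen.

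The size is unknown. The 0.5-1.0 point false difference rests on a 5% true rate in both arms, full experimental capture and 10-20% of control cancers missed. Full experimental capture is the extreme case, and a smaller gap in capture shrinks the effect in proportion. At 90% control capture the false rejection rate is only modestly above nominal (6.6%); at 80% it more than doubles (11.9%). With about 25 cancers per arm a handful of missed cases matters, and the safeguard is cheap enough to be worth adopting.

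**What to change.** In Table 1 and section 4.8 (Collection of Clinical Data), schedule a short cancer-status update for both arms at each 12-month anniversary of randomisation until clinical follow-up ends.

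- Use the same form and dates in both arms, separate from result disclosure.
- Ask about any new cancer, its date, the hospital, and screening or diagnostic investigations since the last form.
- A reported cancer triggers a records request, with a Release of Information form where needed.
- A non-returned form triggers the phone call that section 4.8 already allows and a review of the records the team can access.
- State in section 5.3 that not returning the form is not a ground for withdrawal. Otherwise the new form could itself end outcome collection.

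Cost: an amendment to Table 1 and sections 4.8 and 5.3, and one short form per participant per year. With follow-up of up to 7 years this is at most 7 × 1,000 = 7,000 forms, plus reminders, through REDCap and telephone channels already in use. The downside is a small yearly burden on participants and the reminder work. Clinical management does not change.
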